7.1.9 Mean Daily Glucose and Mean Post-prandial Glucose (Self-monitored)

All subjects will perform a 6-Point SMBG profile for any 3 days (to be included in the calculation of mean daily glucose, the measurements do not need to be recorded over 3 consecutive days, nor do they need to have 3 complete days of measurements.). These are scheduled prior to Day 1 visit (between Week -1 and Day 1) and within a week of Week 52/Study Termination and Rescue or Early Treatment Termination. Blood glucose readings will consist of 3 pre-prandial measurements and 3 post-prandial measurements. Meals are considered to be breakfast, lunch, and dinner. A minimum of 2 days of all 6-point SMBGs are required to complete the 6-point SMBG profile for each period. Similarly, a minimum of 2 days of all post prandial SMBGs will be required for summary of post-prandial averages. The pre-prandial and post-prandial measurements collected at the nominal time points will be considered for analysis.

Glucose concentrations at each of the 6 time points will be averaged over the 3 days to derive the mean glucose concentrations at each of the 6 time points. The mean daily glucose (MDG) will then be calculated as the average over the average glucose concentrations at the 6 time points. Only complete pairs of the average pre-prandial and post-prandial blood glucose values will be used for the calculation. For example, if the available average time point data for a subject at a visit are

pre-breakfast, post-breakfast, and pre-dinner, then the daily average will be calculated as (pre-breakfast + post-breakfast)/2. The average value for pre-dinner is excluded for the calculation since the average value for the post-dinner is missing. The mean post-prandial glucose will be calculated as the average over the average glucose concentrations at the 3 post-prandial time points.

7.1.10 Mean Amplitude of Glucose Excursions (MAGE) of Continuous Glucose Monitoring System Readings

Mean amplitude of glucose excursions (MAGE) is calculated using data from continuous glucose monitoring (CGM). MAGE for a 24-hour period equals “the arithmetic mean of the blood glucose increases or decreases (from blood glucose nadirs to peaks or vice versa) when both ascending and descending segments exceeded the value of one standard deviation of the blood glucose for the same 24-hour period”¹. Therefore, it corresponds to the mean of absolute differences between consecutive maxima and minima, as long as these differences are greater than one standard deviation for the same 24-hour period.

Figure 7.1.3-1 is an example of calculation as described in the original publication of MAGE³.

Figure 7.1.3-1: Blood glucose curve of a subject studied on intermediate-acting insulin regimen.

[figure not shown]

Figure from Service, et al., 1970³

As stated in ³, the calculation of MAGE for subject in Figure 7.1.3-1 “is as follows: the first excursion, 333 to 208 mg./100 mL., is 125 mg./100 mL., exceeding the value of one standard deviation; 62. The first blood glucose increase, from 208 to 322 mg./100 mL, is 114 mg/100 ml [...] and also exceeds one standard deviation; however, the subsequent blood glucose decrease of 35 mg./100 mL (from 322 to 287 mg./100 mL) is less than one standard deviation and so this excursion is not counted. The next blood glucose increase, from 208 to 432 (224 mg./100 mL), and decrease, from 432 to 137 mg./100 mL (295 mg./100 mL), both exceed the value of one standard deviation; therefore this glycemic excursion is 295 because the first excursion is in a peak-to-nadir direction and the direction of calculation (peak-to-nadir or nadir-to-peak) is established, for that CBGA, by the direction of the first excursion.” Continuing, the next peak is 272 mg./100 mL which corresponds to an excursion of 135 mg./100 mL. The next excursion is 116 mg./100 mL to a nadir at 156 mg./100 mL, followed by an excursion of 160 mg./100 mL to a peak at 316 mg./100 mL. The next nadir is at 173 mg./100 mL corresponding to an excursion of 143 mg./100 mL and it is followed by a peak at 322 mg./100 mL and a respective excursion of 149 mg./100 mL and by a nadir at 196 mg./100 mL and a respective excursion of 126 mg./100 mL. The next excursion is 178 mg./100 mL to a peak at 374 mg./100 mL, followed by one of 332 mg./100 mL to a nadir at 42 mg./100 mL and one of 186 mg./100 mL to the subsequent peak of 228 mg./100 mL. Finally, the last couple of excursions are 149 mg./100 mL to the next nadir at 79 mg./100 mL and 163 mg./100 mL to the final peak point at 242 mg./100 mL. Therefore, MAGE for this subject profile corresponds to the arithmetic mean of all excursions and equals approximately 177 mg./100 mL.

Note that despite that this example refers to glucose expressed in mg/dL, calculation of MAGE with glucose readings expressed in standard international units (i.e., mmol/L) will follow the same principle.

For calculating MAGE the following definitions apply:

- **Segment:** the ascending or descending part between a nadir and a peak.
- **Qualifying excursion:** A change from nadir to peak (or from peak to nadir) where both the excursion and the following segment in the opposite direction exceed 1 standard deviation for the whole 24-hour period for the subject.

MAGE is calculated as the arithmetic mean of all qualifying excursion during the 24 hours.

Phase V® is collecting the data for CGM in this study. More details on the collection and analysis is provided in Appendix 1.

7.2 Study Conduct

Subjects who deviate from protocol conditions (e.g., important inclusion/exclusion criteria) will be reported as having significant protocol deviations. Significant protocol deviations that are determined to affect the primary efficacy results are deemed Relevant Protocol Deviations (RPDs). A list of relevant protocol deviation criteria, along with the consequent handling of data should those deviations occur, is given in Table 7.2-1. There will be no data exclusion for significant protocol deviations only.

Table 7.2-1: List of Relevant Protocol Deviations

RPD #	RPD Criteria	Exclusion Type	Exclusion Level
1	Randomized subjects without type 2 diabetes or with central laboratory HbA1c more than 0.2% outside of specified limits of $\geq 7.5\%$ and $\leq 10.5\%$	Complete	This will be assessed using the screening value or at an unscheduled visit prior to randomization.
2	Randomized subjects who did not receive stable dose of metformin	Complete	Subjects not taking ≥ 1500 mg metformin for at least 8 weeks prior to enrollment
3	Randomized subjects with abnormal TSH and free T4 missing or abnormal at enrollment or at an unscheduled visit prior to randomization	Complete	Because the T4 test is collected reactively to TSH, this deviation would only occur if there were an abnormal TSH and free T4 value
4	Randomized subjects with history of hemoglobinopathy, (with the exception of sickle cell trait (SA) or thalassemia minor), and/or chronic or recurrent hemolysis.	Complete	
5	Randomized subjects who used antihyperglycemic medication (other than protocol required medications) for 14 or more consecutive days during the short-term double-blind/ ST + LT treatment period.	Partial /Complete	Exclusion will start from the 14 th consecutive day that the medication was taken/ Subjects who were on treatment < 14 days and used prohibited antihyperglycemic medication will be excluded
6	Randomized subjects that were treated with any systemic corticosteroid therapy for ≥ 5 consecutive days initiated during the short-term double-blind/ST + LT treatment period.	Partial /Complete	Exclusion will start from the 5 th day that the medication was taken. Subjects who were on treatment < 5 days and used prohibited corticosteroid medication will be excluded
7	Randomized subjects who took no dose of metformin or dose of metformin outside dose range for ≥ 2 consecutive weeks in the short-term double-blind/ST + LT treatment period	Partial /Complete	Exclusion will start from the 14 th consecutive day that metformin was either not taken or outside range of ≥ 1500 . Subjects who were on treatment < 14 days and did not take metformin according to protocol will be excluded
8	Randomized subjects who receive no study medication or dosing for ≥ 2 consecutive weeks in the short-term double-blind/ST + LT treatment period	Partial /Complete	Exclusion will start from the 14 th consecutive day that the medication was not taken in an interruption. Subjects who were on treatment < 14 days and did not receive double-blind study medication will be excluded

Table 7.2-1: List of Relevant Protocol Deviations

RPD #	RPD Criteria	Exclusion Type	Exclusion Level
9	Randomized subjects who received incorrect study medication or dosing for ≥ 2 consecutive weeks in the short-term double-blind/ST + LT treatment period	Partial/Complete	Exclusion will start from the 14 th consecutive day that the incorrect medication was taken. Subjects who were on treatment < 14 days and did not receive correct study medication or dosing will be excluded
10	Randomized subjects who are judged to be noncompliant in terms of overall compliance, i.e., who took less than 80% or more than 120% of their prescribed dose of study medication during the short-term double-blind/ST + LT treatment period.	Complete	

7.3 Study Population

7.3.1 Subject Disposition

The disposition of subjects for the screening period, lead-in period, and the 52-week short-term double-blind treatment period will be summarized. The summary of status in the screening period will include all subjects in Enrolled Subjects Data Set. Reasons for discontinuation for subjects who discontinued from the lead-in period and from the short-term double-blind treatment period will be tabulated and listed. The summary will be presented by randomized treatment group and overall.

The summary of status in the long-term treatment period will include all subjects in Randomized Subjects Data Set and be presented by randomized treatment group. This summary will include subjects entering, completing and discontinuing the long-term treatment period with reasons for discontinuation.

7.3.2 Demography and Other Baseline Characteristics

Demographic and other baseline characteristics, including diabetes-related characteristics and renal function characteristics will be summarized overall and by treatment group (where applicable) using the Randomized Subjects Data Set and/or the Evaluable Subjects Data Set, at the ST analysis. At the ST+LT analysis, the demographic and baseline characteristics will be summarized for the Randomized subjects in MRI-PDF sub-study.

Demographic and common baseline characteristics are listed in Table 7.3.2A. Common diabetes related baseline characteristics are listed in Table 7.3.2B. Common renal function baseline characteristics are listed in Table 7.3.2C, and hematuria (other disease characteristics, for ST+LT only) is listed in Table 7.3.2.D.

Table 7.3.2A: Demographic and Common Baseline Characteristics

Characteristic	Summarized as	Categories
Gender	Categorical	Male, Female
Age	Categorical and Continuous	< 65 yrs ≥ 65yrs - <75 ≥75 yrs
Female Age	Categorical	≤ 50 yrs > 50 yrs
Race	Categorical	White, Black or African American, American Indian or Alaska Native, Native Hawaiian or other Pacific Islander, Asian, Other
Ethnicity	Categorical	Hispanic/Latino, Non-Hispanic/Latino
Body Weight	Continuous	-
Height	Continuous	
Body Mass Index	Categorical and Continuous	< 25 kg/m ² ≥ 25 kg/m ² ≥ 27 kg/m ² ≥ 30 kg/m ²
Geographic Region	Categorical	As defined in Appendix 4

Table 7.3.2B: Common Diabetes-Related Baseline Characteristics

Characteristic	Summarized as	Categories
Duration of Type 2 Diabetes	Categorical and Continuous	< 3 yrs ≥ 3 and ≤ 10 yrs > 10 yrs
HbA1c	Categorical and Continuous	<8% ≥ 8 and < 9% ≥ 9%
FPG	Continuous	-

Table 7.3.2C: Common Renal Function Baseline Characteristics

Characteristic	Summarized as	Categories
eGFR (MDRD)	Categorical and Continuous	< 60 mL/min/1.73m ² ≥ 60-< 90 mL/min/1.73m ² ≥ 90 mL/min/1.73m ²

Table 7.3.2D: Hematuria (Other disease characteristics) (ST+LT only)

Characteristic	Summarized as	Categories
Hematuria n (%)	Categorical	Female (Yes, No) Male (Yes, No)

All summaries of continuous characteristics will be based on non-missing observations. For categorical characteristics, percentages will be calculated out of the total number of subjects in the data set, overall, and by treatment group, where applicable (i.e., each denominator includes the number of subjects with missing/unknown values for the characteristic).

7.3.3 Specific and General Disease History

The number (percent) of subjects with diabetes, diabetes-related disease histories will be summarized by treatment group and overall using the Randomized Subjects Data Set for the short-term double-blind treatment period, at the ST analysis. At the ST+LT analysis the demographic and baseline characteristics will be summarized for the Randomized subjects in MRI-PDF sub-study.

The number (percent) of subjects with general medical history findings will also be summarized by treatment group and overall using the Randomized Subjects Data Set for the short-term double-blind treatment period.

7.4 Extent of Exposure

7.4.1 Study and Rescue Medication

The extent of exposure to study medication during the 52-week short-term double-blind treatment period is defined as the difference between the last and the first dose of study medication of the short-term double-blind treatment period plus 1 day. The extent of exposure to study medication will be summarized using the Treated Subjects data set for the short-term double-blind treatment period and the short-term double-blind treatment period prior to rescue as well as regardless of rescue, where the number and percent of subjects with an extent of exposure within specified day ranges (1-6, 7-14, 15-28, 29-42, 43-56, 57-70, 71-84, 85-168, 169-252, 253-336, 337-371, ≥ 372 days) will be presented by treatment group. The mean (SD), median and range of the number of days of exposure will also be presented. Summaries will be presented excluding and including periods of interruptions (defined by record of 0 tablets of study medications on the case report form (CRF)). All rescue medication use during the 52-week short-term double-blind treatment period will be summarized and listed by treatment group.

The extent of exposure to study medication during the combined short- and long-term treatment periods is defined as the difference between the last dose of short-term double-blind or long-term treatment and the first dose of double-blind study medication plus 1 day. For a subject, when there are duplicate records of study medication exposure data within one of the study treatments dispensed (saxagliptin, dapagliflozin, or glimepiride) that have identical start and stop dates and number of pills taken, but different bottle/lot numbers, the average of the pill counts across that date range in the duplicate records will be used to count the number of pills taken for that study

treatment during that date range. The extent of exposure to study medication will be summarized using the Treated Subjects data set for the combined short- and long-term treatment period prior to rescue as well as regardless of rescue. The number and percent of subjects with an extent of exposure within pre-specified day ranges (1-90, 91-180, 181-360, 361-540, 541-720, 721-900, 901-1100 and > 1100 days) will be presented by treatment group. The mean (SD), median, and range of the number of days of exposure will also be presented. Summaries will be presented including periods of interruptions (defined by record of 0 tablets of study medications on the case report form (CRF)). All rescue medication used during the combined short- and long-term treatment periods will be summarized and listed by treatment group.

A listing of subjects by batch number of study medication will also be generated for both the short-term and combined short- and long-term treatment periods.

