4.1 Investigational Product

An investigational product, also known as IMP in some regions, is defined a pharmaceutical form of an active substance or placebo being tested or used as a reference in a clinical study, including products already with a marketing authorization but used or assembled (formulated or packaged) differently than the authorized form, or used for an unauthorized indication, or when used to gain further information about the authorized form.

All study drugs should be kept in a secure place under appropriate storage conditions. The IMP label on the bottle specifies the appropriate storage. It is the responsibility of the investigator to ensure that IMP is only dispensed to study subjects. The IMP must be dispensed only from official study sites by authorized personnel according to local regulations.

In this protocol, IMP(s) is/are: (also described in [Table 4-1](#)) are saxagliptin 5 mg, dapagliflozin 10 mg, glimepiride 1 mg, glimepiride 2 mg, glimepiride 4 mg, and matching placebos. Rescue medication insulin (will be reimbursed) and metformin will not be provided by the Sponsor, since it is part of patient's standard of care.

- Blinded saxagliptin 5 mg and dapagliflozin 10 mg administered orally for the 52 week double - blinded short-term treatment period, and the 104-week subject- and site-blinded long-term treatment period of the study
- Blinded glimepiride 1 mg, 2 mg, 3 mg, 4 mg, or 6 mg administered orally for the 52-week double blinded short-term treatment period, and the 104-week subject- and site-blinded long-term treatment period of the study

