4.4 Method of Assigning Subject Identification

CCI

The content of this section is redacted with two large black rectangular boxes covering the text.

Subjects entering the 52-week double-blinded short-term treatment period

Following completion of the lead-in period, subjects who meet the criteria will be randomly assigned by the IVRS at the Day 1 Randomization visit, to one of the following two (2) double blind treatment arms in a 1:1 ratio:

- Blinded saxagliptin 5 mg and dapagliflozin 10 mg
- Titrated to blinded glimepiride 1 mg, 2 mg, 3 mg, 4 mg, or 6 mg

Randomization schedules for both subject treatment and containers will be generated and kept by the Sponsor.

Subjects entering the 104-week long-term subject- and site-blinded treatment period

Following completion of the 52-week double-blinded treatment period, subjects eligible for the long-term subject- and site-blinded treatment period will be continued in their same randomization assignment based on their original randomization grouping. Subjects that were assigned to be on the blinded saxagliptin 5 mg and dapagliflozin 10 mg arm will continue to receive the blinded saxagliptin 5 mg and dapagliflozin 10 mg. Subjects that were assigned to be on the blinded glimepiride 1 mg, 2 mg, 3 mg, 4 mg, or 6 mg arm will continue to receive blinded glimepiride. At all study visits when study drug is dispensed, each subject will be assigned multiple container numbers by the IVRS. Container numbers will be assigned non-sequentially and will correspond to the numbers printed on the containers and bottles containing study drug, and will be recorded on the appropriate eCRF. The IVRS will be available 24 hours per day, 7 days a week.

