4.5 Selection and Timing of Dose for Each Subject

Saxagliptin 5 mg tablets or matching placebo tablets, will be administered orally once daily for the 156-week treatment period (52 week double-blinded and 104 week subject- and site-blinded treatment periods). Saxagliptin 5 mg is the maximum recommended daily dose. No up- or down-titration of saxagliptin will be allowed.

Dapagliflozin 10 mg tablets or matching placebo tablets, will be administered orally once daily for the 156-week treatment period (52 week double-blinded and 104 week subject- and

site-blinded treatment periods). Dapagliflozin 10 mg is the maximum recommended daily dose. No up- or down-titration of dapagliflozin will be allowed.

Glimepiride 1 mg, 2 mg, and 4 mg tablets and matching placebo capsules, will be administered orally once daily for the 156 week treatment period (52 week double-blinded and 104 week subject- and site-blinded treatment periods). The starting dose for glimepiride is 1 mg per day (once daily), which can be further increased by increments of 1-2 mg at 3-week intervals to a maximum of 6 mg per day in this study. The titration steps will be 2 mg, 3, mg, 4 mg, and 6 mg once daily if needed. In patients for whom titration is not medically indicated at Week 3, re-assessment for titration will occur at Week 6, Week 9, and Week 12. The glimepiride dose can be down-titrated during the titration period if hypoglycemic events occur. The treatment can thereafter be up-titrated once during the titration period. The patients, whose IMP dose was up-titrated to the maximum level, will have a follow-up phone call 3 weeks later. The glimepiride dose can be down-titrated from Week 12 onwards (maintenance period) if hypoglycemic events occur.

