11. [Section 3.5.3](#): Discontinuation Guidelines due to Protocol-Defined Hypoglycemia Episodes and [Section 3.5.4](#): Discontinuation Guidelines due to Ketoacidosis – Text relating to down-titration of blinded study drug and/or background antihyperglycemic agent during the study due to hypoglycemic events moved from [Section 3.5.4](#) to [3.5.3](#). Clarified that the background antihyperglycemic agent related to metformin which can be down-titrated if hypoglycemic events occur, but that the dose of metformin must be ≥ 1500 mg/day, unless metformin treatment is temporarily withheld due to $\text{CrCl} < 60$ mL/min (estimated by Cockcroft-Gault).
12. [Section 3.5.4](#): Discontinuation Guidelines due to Ketoacidosis – Cross-reference added to [Section 7.3](#), providing details of DKA event recording and adjudication.
13. [Section 3.7](#): End of Study – New section added to define the end of the study.
14. [Section 4](#): Study Drug, [Table 4-1](#): Study Drugs for CV181365: Product Description: Short-term Double-Blinded Treatment Period and Long-term Subject- and Site-Blinded Treatment Period and [Section 4.1](#): Investigational Product – Storage conditions updated.
15. [Section 4](#): Study Drug, [Table 4-2](#) and [Section 4.1](#): Investigational Product: Contents of Blinded Glimperide 2-Bottle kit – Table deleted and reference to [Table 4-2](#) removed.
16. [Section 5.2](#): Study Materials – Confirmation that a DKA Adjudication Manual for Sites will be provided.
17. [Section 5.8.6](#): Magnetic Resonance Imaging (MRI) - Clarified that a) during the short-term treatment period, the MRI results will be blinded to recruiting sites, investigators, the MRI sites, the subjects, and the Sponsor, but would not be blinded to the Sponsor after Week 52, b) the Sponsor will not provide MRI results to subjects or investigators at the conclusion of the study, unless specifically requested by the subject, and c) MRI analysis will be performed using semi-automated software.
18. [Section 5.9](#): Results of Central Assessments and [Appendix 2](#): Central Laboratory Results – Clarified which laboratory results were blinded in either the short or long term treatment periods during the study.
19. [Section 6.2.1](#): Non-serious Adverse Event Collection and Reporting – Clarified the collection and reporting of AEs.

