7.4.3 Measurements of Treatment Compliance

Percent treatment compliance will be calculated for the short-term and the combined short- and long-term treatment period for each treatment group. For each subject, percent compliance is defined as the total number of tablets taken divided by the total number of tablets that should have been taken, multiplied by 100. A subject is considered compliant if percent compliance is $\geq 80\%$ and $\leq 120\%$. The number and percent of subjects considered compliant will be summarized for each treatment group using the Treated Subjects data set.

For the short-term:

The number of tablets that should have been taken is calculated as 1 + the number of days from the first short-term double-blind treatment period dose recorded in the “Record of Study Medication” to the last short-term double-blind treatment dose, times the prescribed daily dose (i.e., 2 tablets per day, one from each bottle). The number of tablets taken is the total number of

tablets recorded (sum of bottle 1 and bottle 2) as taken based on the CRF, summed over the days counted when calculating the number of tablets that should have been taken, including the day of the last short-term double-blind treatment dose.

For the combined short- and long-term:

The number of tablets that should have been taken is calculated as 1 + the number of days from the first treatment period dose recorded in the “Record of Study Medication” to the last treatment dose, times the prescribed daily dose (i.e., 2 tablets per day, one from each bottle). The number of tablets taken is the total number of tablets recorded (sum of bottle 1 and bottle 2) as taken based on the CRF, summed over the days counted when calculating the number of tablets that should have been taken, including the day of the last treatment dose (following any adjustments for duplicate records as described in Section 7.4.1)..

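### The combined-period rule for duplicate dosing records (SAP 7.4.1) can count a correct two-capsule glimepiride dose as one capsule and so report false non-compliance

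*SAP*

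**What the plan says.** **The rule.** SAP 7.4.1, in its paragraph on the combined short- and long-term periods, covers duplicate records "within one of the study treatments dispensed (saxagliptin, dapagliflozin, or glimepiride". For records "that have identical start and stop dates and number of pills taken, but different bottle/lot numbers, the average of the pill counts" over that date range stands as the number taken. No other test for a duplicate is given. The SAP amendment history places this handling at the combined-period analysis.

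**The supply.** Protocol 4.1 lists the comparator product as "glimepiride 1 mg, glimepiride 2 mg, glimepiride 4 mg, and matching placebos"; Table 4-1 gives the same three active strengths. Protocol 4.5 starts at 1 mg and continues: "The titration steps will be 2 mg, 3, mg, 4 mg, and 6 mg once daily if needed". Under Protocol 4.4, whenever drug is dispensed "each subject will be assigned multiple container numbers by the IVRS", and those numbers go on the eCRF.

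**The use of the count.** SAP 7.4.3 defines compliance as tablets taken over tablets due, with an acceptable range of 80% to 120%. Tablets taken are added over two numbered bottles, and tablets due are two a day, one per bottle. For the combined periods the count is taken "following any adjustments for duplicate records as described in Section 7.4.1". In SAP Table 7.2-1, relevant protocol deviation (RPD) 10 covers subjects "who took less than 80% or more than 120% of their prescribed dose of study medication". SAP 6.3.5 says that RPDs will be summarized for the combined period but that no evaluable population will be.

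**The concern.** The rule recognizes a duplicate by a pattern that correct dosing can also produce. A subject on 3 mg or 6 mg who takes one capsule a day from each of two bottles has two glimepiride lines with equal dates, equal counts and different bottle numbers. The rule treats the second line as a repeat of the first, although it is the other half of the dose.

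The two SAP sections also pull in opposite directions: 7.4.3 adds across bottles, while the adjustment it imports from 7.4.1 averages across them. At stake is whether the final report shows adherent subjects as non-compliant, both in the compliance table and among the relevant deviations.

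**Working it through.** The plan states no figure to reproduce. The check applies its rules to a fully adherent subject.

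**1. Capsules needed.** From strengths of 1, 2 and 4 mg, using at most three capsules:
- 3 mg = 1+2 or 1+1+1
- 6 mg = 2+4, 1+1+4 or 2+2+2

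The only two-capsule solutions are 1+2 and 2+4. Each uses two strengths and hence two bottles.

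**2. Effect of averaging.** The rule applies only when the counts are equal. Two lines of n pills become (n + n)/2 = n, where the true total is 2n. One capsule a day from each bottle is therefore counted as 1 a day instead of 2.

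**3. Effect on compliance.** SAP 7.4.3 does not say which products its two bottles hold, so the result depends on the reading. For a subject on a two-capsule dose throughout:

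| Reading of 7.4.3 | Without averaging | With averaging |
|---|---|---|
| The two bottles are glimepiride, 2 due per day | 2/2 = 100% | 1/2 = 50% |
| All products pooled, pills actually due (1 saxagliptin + 1 dapagliflozin + 2 glimepiride = 4) | 4/4 = 100% | 3/4 = 75% |
| All products pooled, fixed 2 due per day | 4/2 = 200% | 3/2 = 150% |
| Saxagliptin and dapagliflozin only, 2 due per day | 2/2 = 100% | 2/2 = 100% |

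Averaging alone moves an adherent subject outside 80% to 120% on the first two readings. On the third the subject is outside the range either way. On the fourth nothing changes.

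**4. A subject who climbs the whole ladder.** Assume one capsule at 1, 2 and 4 mg and two at 3 and 6 mg, with a step every 3 weeks and 6 mg from Week 12 to Week 156 (1092 days in all).
- One-capsule days: 3 × 21 = 63. Two-capsule days: 21 at 3 mg and 144 × 7 = 1008 at 6 mg.
- Pooled pills due: 3 × 63 + 4 × 21 + 4 × 1008 = 189 + 84 + 4032 = 4305.
- Counted after averaging: 3 × 1092 = 3276.
- Compliance: 3276/4305 = 76.1%.
- Against a fixed 2 per day (2184 due): 3276/2184 = 150% with averaging and 4305/2184 = 197% without.

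**5. Share of days needed to fall below 80%.** Let f be the fraction of days on a two-capsule dose recorded as one line per bottle.
- Glimepiride alone, 1 or 2 due as assigned: 1/(1+f) < 0.8 when f > 0.25.
- Glimepiride alone, 2 due every day: (2−f)/2 < 0.8 when f > 0.40.
- Pooled, 3 or 4 due as assigned: 3/(3+f) < 0.8 when f > 0.75. The ladder subject has f = (21 + 1008)/1092 = 0.94.

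**6. Reach.** The short-term compliance paragraph in 7.4.3 does not use the adjustment. Extent of exposure in 7.4.1 is last dose date minus first plus one day, so pill counts do not enter. First and last dose dates in SAP 8.6 need only a count above zero, and the average of two equal positive counts stays above zero.

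**The case against.** The strongest objection is that the eCRF is not shown. The under-count occurs only if each line holds the pills taken from that bottle. If each line carries the product total, a 6 mg subject has 2 on both lines; averaging then gives the correct 2 and summing would give 4. This stands as a condition. The addition over two bottles in 7.4.3 favours one line per bottle but does not prove it. The summary of changes for Amendment 05 records the deletion of a table headed "Contents of Blinded Glimperide 2-Bottle kit"; that is consistent with two-bottle dosing, but it is superseded text and carries no weight here.

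Second, repeated entries under different bottle numbers can be genuine, since several containers are assigned at a dispensing. The rule may be meant for records already identified as duplicates. That is a fair reason to keep a rule, but as written it offers no way to tell a repeat from the other half of a dose.

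Third, the 75% and 76.1% figures use 3 or 4 pills due per day, whereas 7.4.3 fixes 2. This also stands, and is why the effect is given by reading.

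A reader might infer a bias between arms, because FPG-driven titration may take the arms to different doses. The documents do not support that. Placebo capsules are titrated too, and no section states how many capsules make up 1, 2 or 4 mg. If every dose is one capsule from each of two bottles, the count does not vary with dose at all. A reader might also infer damage to the Week 52 per-protocol result; the rule belongs to the combined-period analysis, which has no evaluable population.

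**Conclusion.** The concern holds in a limited form. As written, the rule in SAP 7.4.1 takes a correct 1+2 mg or 2+4 mg dose for a duplicate and halves its count, provided the eCRF has one line per bottle. It also conflicts with the addition across bottles in 7.4.3.

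That every adherent 3 mg or 6 mg subject will be labelled non-compliant is more than the documents show: the label depends on which products and which denominator 7.4.3 intends, and on the share of days at a two-capsule dose. The possible harm is false non-compliance in two descriptive outputs, the combined-period compliance table and the combined-period RPD 10 summary. The Week 52 analyses, the evaluable set, days of exposure and the first and last dose dates are unaffected. Whether the arms would differ cannot be determined. This should be corrected, but no efficacy conclusion depends on it.

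**What to change.** First confirm that each eCRF dosing line records the pills from that bottle only. If it does, amend the SAP as follows.

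- **7.4.1:** limit averaging to verified duplicates, meaning records of the same product and the same strength or kit position, or records whose summed count exceeds the number of capsules assigned in the IVRS for those dates. Otherwise sum glimepiride/placebo counts across the bottles that make up one assigned dose.
- **7.4.3 and RPD 10:** use that count, name the products covered, and define pills due by product and assigned number of capsules.

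With these changes a fully adherent 3 mg or 6 mg subject scores 2/2 = 100% for glimepiride and 4/4 = 100% pooled. SAP 8.6 needs no change.

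The cost is a short SAP edit and a revised derivation. Container numbers are already on the eCRF and containers are assigned through the IVRS. Nothing changes for subjects or sites.
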